Recruitment goals for the 510(k) phase of the study are at least 100 specimens positive for CT, 100 specimens positive for TV, and 45 specimens positive for NG as determined by PIS. Recruitment goals for the CLIA waiver phase of the study are 120 positive specimens for CT and TV (prospective), and 45 positive specimens for NG. In order to achieve the required precision for sensitivity of NG detection, additional specimens may be required. Banked NG positive specimens may also be used and will be provided to the testing sites for Click device testing. Thus, the maximum target for the number of PIS-positive NG samples is 85. At specified enrollment targets, the sensitivity of the Click device with respect to NG will be estimated. If the NG estimate meets the requirements for the 510(k) and CLIA waiver phases at any of the interim points and the enrollment targets for CT and TV have been met, collection of samples will stop. Otherwise, collection of samples will continue. See section 7 for details on the interim reviews. At least 30% of total samples must be from sites considered low prevalence. All comparator tests will be performed by a reference laboratory.

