5.4.1 Inclusion Criteria

1. Vaginal specimen is from a female age ≥ 14 years at the time of specimen collection.
2. A minimum of 2.0 mL of frozen sample taken from well-characterized specimens collected from known NG subjects not being treated since testing positive within the past 4 months.
3. NG comparator results available.
4. Vaginal specimen is obtained from a collection wherein the subject consented/assented to future unspecified research use of her specimen.

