6.7.1 Device Accountability

Click Diagnostics will provide the Click devices.

Each clinical site will be responsible for documenting the receipt, storage, use, and disposition of Investigational Use Only devices throughout the study. Records must be available for inspection by the DMID monitoring contractors. Used devices will be returned to Click per the MOP. The Monitors will not physically check the used Click devices. They may be returned prior to

monitoring of the device accountability logs, but must be logged according to the MOP. At the discretion of Click, remaining unused study supplies provided by Click may be returned at the conclusion of the study.

6.8 Study Procedures for Click Device Testing of Banked Specimens Collected from Known NG-Positive Subjects

If additional NG+ samples are needed, Click will provide banked specimens to the clinical sites according to the MOP.

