7.2 Sample Size Considerations

Recruitment goals for the 510(k) phase of the study are at least 100 specimens positive for each of CT and TV, and at least 45 specimens positive for NG, as determined by PIS. Recruitment goals for the CLIA waiver phase of the study are 120 positive specimens for each of CT, TV, and 45 NG. Approximately 585 subjects will be recruited from low-prevalence sites (one third of the 1,750) and approximately 1165 subjects will be recruited from high prevalence sites. The average expected proportion of samples positive via PIS for CT, TV, and NG among subjects enrolled at the high prevalence sites are, respectively, 12.4%, 19.5%, and 8.1%. The corresponding estimates for the low-prevalence sites are 1.7%, 1.0%, and 1.4%. Based on these prevalence estimates, it is expected that the enrollment targets will be met for the three organisms. Thus, the study as designed is expected to meet the 510(k) and CLIA waiver recruitment goals for all three organisms. If NG prevalence is lower than expected, banked NG+ samples may need to be leveraged to meet the recruitment goals for NG. As indeterminate PIS results or invalid or failed Click device results are expected for a small number of cases, enrollment may extend beyond 1750 to replace these results. The duration of enrollment may be extended if the actual prevalence of any of the organisms is lower than predicted.

For the estimation of the sensitivity and specificity of the Click device, we assume both the sensitivity and specificity is at least 95%. For 510(k) clearance, the study aims to demonstrate that sensitivity to each of CT and NG is at least 95%, with a lower bound of the two-sided 95% Wilson Score confidence intervals at least 90%, and to demonstrate that sensitivity to TV is at least 95%, with a lower bound of the two-sided 95% Wilson Score confidence intervals at least 85%. Regarding specificity, the study aims to demonstrate specificity to each of CT, TV, and NG is at least 95%, with a lower bound of the two-sided 95% Wilson Score confidence intervals at least 90%. For the CLIA waiver, the study aims to demonstrate that both the sensitivity and specificity to each of CT, TV, and NG is at least 95%, with a lower bound of the two-sided 95% Wilson Score confidence intervals at least 89%.

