7.3 Planned Interim Reports

Interim reports may be generated during the course of the study. The reports will only be made available to the Sponsor team and Click Diagnostics for the purpose of submission to the FDA. The study operators and laboratory staff that run the assays will not have access to the reports. The study statistician will provide the reports, which will contain summaries from analyses outlined in section 7.4 and detailed in the separate Statistical Analysis Plan.

The reports will be generated after the data are entered in the database; the approximate milestones for the generation of each report are provided in Table 5 below:

Table 5. Types of Study Reports and Schedule

Report Type	Milestone
Interim Report ¹	After the collection of 50 PIS-positive CT samples, 50 PIS-positive TV samples, 20 PIS-positive prospectively collected NG samples
510(k) Report	After the collection of 100 PIS-positive CT samples, 100 PIS-positive TV samples, ≥45 PIS-positive prospectively collected NG samples
CLIA Waiver Report	After the collection of 120 PIS-positive CT samples, 120 PIS-positive TV samples, ≥45 PIS-positive prospectively collected NG samples

¹The need for this interim report depends on the rate of enrollment of subjects with PIS-positive NG samples. The report will be generated if it is possible to do so without halting enrollment and/or losing momentum in accrual or if the rate of enrollment of subjects who are PIS-positive NG is such it is expected that multiple NG milestones will not be met in a short period of time.

It is not anticipated that the study or its operations will be impacted by the analyses performed for the interim report (e.g., early termination of the study), but instead the report fulfills a regulatory requirement and provides the FDA an update on the progress of the trial. As such, adjustments for the multiple interim calculations of interval estimates are not planned.

The 510(k) and CLIA Waiver reports will be generated once the NG enrollment has finished per the enrollment procedure outlined in section 7.2. Though it is possible that NG sensitivity will be estimated multiple times, no adjustments for the multiple calculations are planned.

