7.3.1 Ongoing Investigative Product Performance Tracking

The primary analysis of agreement of Click Sexual Health Test results compared to PIS will be performed as described in section 7.4.3 and as shown in the example 2 x 2 contingency table depicted in Figure 6 of this protocol on an ongoing basis during the course of the study. These analyses will track performance of the investigative device and thereby serve to inform the Sponsor team and Click Diagnostics as to the likelihood of successful completion of the study with performance conforming to acceptance criteria, or conversely, to eventual futility of the study for failure to achieve acceptable performance. In no case shall the results of these ongoing analyses initiate an early termination of the study for

benefit, i.e. based upon early achievement of acceptable performance.

In accord with DMID Policy, analysis results shall be distributed only to the Sponsor team and to Click Diagnostics and the receiving personnel shall not further distribute the results. No results shall be supplied to study site personnel or to study monitors, and neither the raw data nor the analysis of these ongoing analyses shall be submitted to FDA. Study updates will only be provided to the FDA at timepoints listed in Table 5 above. The results of these ongoing analyses shall not translate into study design changes, protocol amendments, or investigative device design changes. As such, no adjustments for the multiple analysis will be made.

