7.4.1 Analysis Populations

The following analysis populations will be defined separately for each report (Interim, 510(k), CLIA Waiver). The statistical analysis plan will include the further details on the definitions of the report-specific analysis populations.

Enrolled Population: This population includes all participants enrolled at the time of the data cut-off for the report.

Evaluable Population: This population includes all samples available at the time of the data cut-off for the report, which provide an evaluable Click Diagnostics Sexual Health Test result and an evaluable PIS result for each tested pathogen (CT, NG, TV). There will be a separate Evaluable population for each organism.

A sample provides an evaluable result if both the Click device and the PIS provide a valid positive or negative result.

The primary outcome measure of sensitivity and specificity of the Click Diagnostics Sexual Health Test will be evaluated in the evaluable population.

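### Protocol 7.2 and Table 5 disagree on whether banked NG positives count toward the 45, and the protocol and SAP disagree on whether they enter the primary NG estimate

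*Protocol*

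**What the plan says.** **The goal.** Protocol 7.2 sets the 510(k) NG goal at "at least 45 specimens positive for NG, as determined by PIS". Protocol 4 gives the CLIA waiver goals as "120 positive specimens for CT and TV (prospective), and 45 positive specimens for NG", attaching the word prospective to CT and TV only. Protocol 7.2 then adds: "If NG prevalence is lower than expected, banked NG+ samples may need to be leveraged to meet the recruitment goals for NG". SAP 5 repeats this. Protocol 4 also allows banked NG specimens where more are needed for precision, up to 85 PIS-positive NG samples.

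**The report trigger.** Table 5 in protocol 7.3 requires "≥45 PIS-positive prospectively collected NG samples" for both the 510(k) and the CLIA waiver report.

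**The specimens.** Protocol 5.4.1 asks for a vaginal specimen from a female aged 14 or over, at least 2.0 mL frozen, from a known and untreated NG-positive subject, with consent to future use and "NG comparator results available". Protocol 6.8 states: "If additional NG+ samples are needed, Click will provide banked specimens to the clinical sites according to the MOP".

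**The analysis set.** Protocol 7.4.1 describes the evaluable population thus: "This population includes all samples available at the time of the data cut-off for the report", subject to a valid Click result and a valid PIS. SAP 6.2.2 limits it to enrolled subjects with both valid results, and excludes any Click specimen tested more than 2 hours after collection.

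**The estimand.** The primary NG outcome (protocol 3.3.4.2, SAP 3.2.1) is sensitivity and specificity in self-collected specimens against a PIS from HCP-collected swabs.

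**The concern.** NG sensitivity is a primary claim with a pass rule: an estimate of at least 95%, with a Wilson lower bound of at least 90% for the 510(k) and 89% for the CLIA waiver. Under protocol 7.2, collection goes beyond 45 when the NG estimate has fallen short, and banked specimens are one permitted source of the extra positives. If they enter the primary estimate, specimens already known to be positive are added after a disappointing result, and they may differ from the prospective ones in collection method and spectrum. If they are easier to detect, the pooled sensitivity is biased upward for the stated target. If they are harder to detect, the bias runs the other way. Because only positives are added, NG prevalence and PPV in a pooled 2x2 table would also lose their meaning.

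The conflict has an operational side too. If NG yield stays below 45, protocol 7.2 would treat the goal as met with banked specimens, while the Table 5 trigger for both regulatory reports would still be unmet.

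**Working it through.** **1. Reproduce Table 4.** With n positives, p the observed sensitivity and z = 1.96, the Wilson lower bound is [p + z²/(2n) − z·√(p(1−p)/n + z²/(4n²))] / (1 + z²/n).

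- 45/45: 100%, lower bound 92.1%
- 42/45: 93.3%, lower bound 82.1%
- 54/55: 98.2%, lower bound 90.4%
- 68/70: 97.1%, lower bound 90.2%
- 82/85: 96.5%, lower bound 90.1%

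These agree with Table 4. One more false negative at each size gives 88.4%, 87.7%, 88.1% and 88.5%, all under 89%. So the 510(k) and CLIA waiver rules have the same limits for NG: at most 0/45, 1/55, 2/70 or 3/85 false negatives.

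**2. How many prospective NG positives does the plan expect?** Protocol 7.2 gives 1165 subjects at 8.1% and 585 at 1.4%.

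- 1165 × 0.081 + 585 × 0.014 = 94.4 + 8.2 = 102.6, or 102.6/1750 = 5.86% overall.
- Banked specimens are needed at 1750 subjects only if overall prevalence is below 45/1750 = 2.57% (44% of planned yield) to reach 45, or below 85/1750 = 4.86% (83% of planned yield) to reach 85.

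**3. How large could the banked share be?** If Table 5 governs, at most 85 − 45 = 40 of 85, or 47%. If protocol 7.2 governs, the goal carries no prospective minimum.

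**4. Extreme case (assumed split and detection).** Take 45 prospective positives with 3 false negatives: 93.3%, lower bound 82.1%, a fail. Add 40 banked positives, all detected: 82/85 = 96.5%, lower bound 90.1%, a pass.

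**5. Pass chance in that same setting.** Assume 45 prospective positives, then banked only, with looks at 45, 55, 70 and 85, limits 0, 1, 2 and 3, and stopping possible at each look. The chance is a sequential binomial sum over the four looks.

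| Prospective sensitivity | All prospective | Banked detected at 98% | Banked detected at 100% |
|---|---|---|---|
| 90% | 4.4% | 22% | 33% |
| 93% | 19% | 45% | 61% |

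The documents give no banked detection rate; 98% and 100% are assumptions.

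**6. The same question near planned yield.** Overall CT prevalence is (1165 × 0.124 + 585 × 0.017)/1750 = 154.4/1750 = 8.82%, so 120 CT positives take about 120/0.0882 ≈ 1,360 subjects. By then NG has about 1,360 × 0.0586 ≈ 80 positives. With 80 prospective and 5 banked, a single look at 85, and every banked specimen detected, the pass chance goes from 2.5% to 3.5% at 90% sensitivity and from 15% to 18% at 93%.

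**7. The populations side by side.** A frozen banked specimen with a valid Click result and a PIS fits protocol 7.4.1. Under SAP 6.2.2 it fails twice: its donor is not an enrolled subject, and it cannot have been tested within 2 hours of collection. Yet SAP 4.2 and SAP 5 carry the banked eligibility and use, and SAP 12 says its analyses coincide with the protocol's. The primary NG table (SAP Table 22) and the breakdowns in SAP Tables 31 to 35 have no row for specimen source.

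**The case against.** The strongest reply is that banked specimens will probably not be used. The plan expects more NG positives than its maximum of 85, collection cannot stop until the CT and TV targets are met, and protocol 7.2 also allows enrollment to be extended. Steps 2 and 6 bear this out: near planned yield the effect is small, and the large shifts in step 5 need 40 banked specimens. This stands, and it makes the point conditional.

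A second reply is that protocol 4 can be read as 45 prospective positives plus a banked top-up, which agrees with Table 5. That reading is reasonable, but protocol 7.2 and SAP 5 say that banked samples may meet the goal itself, so the text still needs aligning.

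Three stronger inferences are tempting and go too far:

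- *Banked specimens need no PIS.* The eligibility list does not name one, but the 510(k) goal, the maximum of 85, Table 4 and both evaluable definitions do. What is missing is a route by which a banked specimen gets its PIS.
- *The final NG claim will pool them.* That follows from protocol 7.4.1 but not from SAP 6.2.2 as written.
- *Operators will recognise them, or the manufacturer will choose them in light of results.* The manufacturer supplies the specimens and receives the ongoing results ("analysis results shall be distributed only to the Sponsor team and to Click Diagnostics", protocol 7.3.1). However, supply follows the MOP, which is not available here and may set coding and selection, and 7.3.1 bars those results from changing the design. The documents do not establish either problem.

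**Conclusion.** The point holds as a set of unreconciled rules about banked NG specimens: whether they count toward the 45, whether they enter the primary estimate, whether they must be self-collected, and how they receive a PIS. With no analysis by specimen source, a reader of the final tables could not tell how much of an NG result came from them.

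The effect ranges from none at planned yield (about 103 prospective positives) to a change from fail to pass in the extreme case (42/45 to 82/85). The extreme case assumes that NG yield stalls at 45, that all 40 further positives are banked, that they are pooled, and that all are detected. The documents do not support a claim that the NG result will rest on banked specimens; they leave that possibility open. It is worth closing before the first NG look, because protocol 7.2 itself cites difficulty in recruiting NG-positive subjects.

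**What to change.** 1. Align protocol 7.2 and SAP 5 with Table 5, so that the NG goal of 45 and the first NG look count prospective PIS-positives only.
2. Make prospective, self-collected specimens the primary NG estimate. Show banked specimens in a separate row, with the combined figure as supplementary.
3. State in protocol 5.4.1 and SAP 6.2.2 that a banked specimen enters the combined figure only if it was self-collected and is PIS-positive under the Table 1 algorithm. State how the enrolled-subject and 2-hour rules apply to it.

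Selection of banked specimens by the SDCC from a list fixed before the first NG look, and coding them among banked negatives, are optional; the MOP may already cover handling.

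The cost is protocol and SAP wording and one table row. The downside is a wider primary NG interval if banked specimens turn out to be needed, since that interval would rest on fewer positives.

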To demonstrate this for CT and TV, 95% Wilson Score confidence intervals were calculated for a range of sample sizes, number of PIS-positive samples, and sensitivity/specificity estimates. Given the uncertainty in the exact number of subjects enrolled or PIS-positive samples, the following parameter ranges were explored: total sample sizes of 1500 to 2000, 100 to 200 PIS-positive samples, and sensitivity/specificity estimates of 95% to 99%. Wilson Score confidence intervals were calculated for each combination of sample size, number of PIS-positive samples, and sensitivity/specificity. As an example, Table 3 below displays the lower confidence bound using a sample size of 1750 and a select subset of the number of PIS-positive samples.

Table 3: Lower 95% Wilson Score Confidence Bounds (%) for Various Number of PIS-Positive Samples and Sensitivity and Specificity Values

Number of PIS-Positive Samples	Sensitivity (%)					Specificity (%)				
	95	96	97	98	99	95	96	97	98	99
100	88.8	90.2	91.5	93.0	94.6	93.9	94.9	96.1	97.2	98.4
101	88.9	90.3	91.6	93.1	94.6	93.9	95.0	96.1	97.3	98.4
102	89.0	90.3	91.7	93.1	94.7	93.9	95.0	96.1	97.3	98.4
103	89.1	90.4	91.8	93.2	94.7	93.9	95.0	96.1	97.3	98.4
104	89.2	90.5	91.9	93.3	94.8	93.9	95.0	96.1	97.3	98.4
105	89.3	90.6	91.9	93.3	94.8	93.9	95.0	96.1	97.3	98.4
106	89.4	90.7	92.0	93.4	94.8	93.9	95.0	96.1	97.3	98.4
120	89.5	91.7	92.9	94.1	95.4	93.9	94.9	96.1	97.2	98.4
121	89.6	91.8	93.0	94.2	95.5	93.9	94.9	96.1	97.2	98.4
122	89.7	91.9	93.0	94.2	95.5	93.9	94.9	96.1	97.2	98.4
123	89.8	91.9	93.1	94.3	95.5	93.9	94.9	96.1	97.2	98.4
124	89.8	92.0	93.1	94.3	95.6	93.9	94.9	96.1	97.2	98.4
125	89.9	91.0	93.2	94.4	95.6	93.8	94.9	96.1	97.2	98.4
126	90.0	91.0	93.2	94.4	95.6	93.8	95.0	96.1	97.2	98.4

Over the entire ranges of parameter values explored, the lower bound of the specificity confidence interval never fell below 93.6%. The lower bound of the sensitivity confidence intervals never fell below 88.8% and was greater than or equal to 89% for all combinations of parameter values except for the following scenario:

- Sample Size = Any, Number of PIS-positive samples = 100 or 101, Sensitivity = 95%

The lower bound of the sensitivity confidence intervals was greater than or equal to 90% for all combinations of parameter values except for the following scenarios:

- Sample Size = Any, Number of PIS-positive samples = 100 to 112, Sensitivity = 95%
- Sample Size = Any, Number of PIS-positive samples = 120 to 126, Sensitivity = 95%

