Thus, apart from a few scenarios, assuming the sensitivity/specificity of the Click device is at least 95%, the study as planned should be able to meet the confidence interval estimate requirements for 510(k) clearance and CLIA waiver for CT and TV.

For NG, the minimum number of PIS-positive samples required for the 510(k) and CLIA Waiver reports is 45. The planned maximum sample size for NG-positive samples is 85. Due to the small 510(k) and CLIA Waiver enrollment targets for NG and the difficulty in recruiting NG-positive subjects, reviews of the sensitivity of the Click device with regard to NG detection will occur at specified enrollment targets to ensure adequate precision of the estimate is achieved while allowing for the collection of samples to stop early if further NG sample collection is not necessary and the enrollment targets for CT and TV have already been met.

The first enrollment target at which sensitivity will be estimated is 45 PIS-positive NG samples. If the 510(k) and CLIA Waiver estimate requirements are met and the enrollment targets for CT and TV have already been met, then collection of NG samples will stop. If the estimate requirements are not met, then collection of samples may proceed to the next enrollment target, as described in Table 4.

Note that, per Table 5 in section 7.3, an interim report will be provided to the FDA after the collection of 50 PIS-positive CT samples, 50 PIS-positive TV samples, and 20 PIS-positive prospectively collected NG samples. The results presented in this interim report will not impact the operations of the study.

Table 4: NG Sensitivity Estimates for Various Interim Sample Sizes

Enrollment Target (Number of PIS- positive NG samples)	Number of False Negatives	Sensitivity Estimate (Lower 95% confidence bound)
45	0	100% (92.1%)
	1	97.8% (88.4%)
	2	95.6% (85.2%)
	3	93.3% (82.1%)
	>3	≤91.1% (≤79.3%)
55	1	98.2% (90.4%)
	2	96.4% (87.7%)
	3	94.5% (85.2%)
	>3	≤92.7% (≤82.7%)
70	2	97.1% (90.2%)
	3	95.7% (88.1%)
	>3	≤94.3% (≤86.2%)
85	3	96.5% (90.1%)
	4	95.3% (88.5%)
	>4	≤94.1% (≤87.0%)

Assessment of the specificity requirement for NG follows similarly to our investigation of specificity for CT and TV above; the study as planned should be able to meet the confidence interval estimate requirements for 510(k) clearance and CLIA waiver for NG.

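### Protocol 7.2 and SAP 5 compute bounds at fixed observed sensitivities, then infer that a device of at least 95% true sensitivity should meet the CT and TV requirements; for CT near 95-96% that inference fails

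*Protocol*

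**What the plan says.** Protocol 7.2, repeated in SAP 5, starts from a planning premise about the device: "we assume both the sensitivity and specificity is at least 95" percent. It sets two counts. "Recruitment goals for the 510(k) phase of the study are at least 100 specimens positive for each of CT and TV"; "Recruitment goals for the CLIA waiver phase of the study are 120 positive specimens for each of CT, TV". For 510(k), the stated sensitivity target reads: "each of CT and NG is at least 95%, with a lower bound of the two-sided 95% Wilson Score confidence intervals at least 90" percent; for TV the bound is 85%. For the CLIA waiver it requires 95% for all three organisms, "with a lower bound of the two-sided 95% Wilson Score confidence intervals at least 89" percent.

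The supporting calculation covers "100 to 200 PIS-positive samples, and sensitivity/specificity estimates of 95% to 99" percent, with total sample sizes of 1500 to 2000. Protocol Table 3 (SAP Table 2) prints a subset. The text then lists the cells that miss 90%, the first being "Sample Size = Any, Number of PIS-positive samples = 100 to 112, Sensitivity = 95" percent and the second 120 to 126 positives at 95%. Only 100 and 101 positives at 95% miss 89%. The conclusion follows: "apart from a few scenarios, assuming the sensitivity/specificity of the Click device is at least 95%, the study as planned should be able to" satisfy the 510(k) and CLIA interval requirements for CT and TV.

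Protocol 7.1 says that there is no formal hypothesis test and that the study is sized for precision. Neither document gives a probability of meeting any bound.

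**The concern.** The grid fixes the observed estimate, while the conclusion is conditioned on the sensitivity of the device. If true sensitivity is 95%, the observed value will often be lower, and a few extra false negatives move the Wilson bound below 90%. The listed exceptions cover counts at which an observed 95% misses the bound. They say nothing about how often a 95% device yields an estimate good enough to pass.

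This text is where the plan says that its CT and TV positive counts suffice. A sponsor or regulator would take from it that a device at the assumed performance should pass outside a short list of counts. If the chance is well below that, the plan states a property that its design does not have.

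**Working it through.** **Inputs** (Protocol 7.2, same in SAP 5): two-sided 95% Wilson interval; goals of 100 (510(k)) and 120 (CLIA) positives; sensitivity bounds of 90% (CT 510(k)), 85% (TV 510(k)) and 89% (CLIA); 1165 subjects at high-prevalence sites (CT 12.4%, TV 19.5%) and 585 at low-prevalence sites (CT 1.7%, TV 1.0%).

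**1. Reproduce the plan.** With z = 1.96 and observed proportion p,

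L = [p + z²/2n − z√(p(1−p)/n + z²/4n²)] / (1 + z²/n).

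For 95 of 100: (0.9692 − 0.0468)/1.0384 = 88.8%, as printed. For 96 of 100: (0.9792 − 0.0429)/1.0384 = 90.2%, as printed. With true positives rounded up to a whole count, all 14 printed rows and both exception lists are reproduced. The lists leave 81 of the 101 counts from 100 to 200 treated as passing 90%.

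**2. Largest number of false negatives that passes.**
- n=100, 90%: 4 (4 gives 90.16%, 5 gives 88.82%).
- n=120, 89%: 6 (bound 89.52%).
- n=100, 85%: 8 (bound just over 85.0%).
- n=152, 90%: 7. n=154, 90%: 8 (8 gives 90.08%, 9 gives 89.27%).

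**3. Chance of passing.** For true sensitivity s, this is P(FN ≤ maximum), with FN ~ Binomial(n, 1−s).

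**4. Expected counts.** CT: 1165×0.124 + 585×0.017 = 144.5 + 9.9 = 154.4. TV: 1165×0.195 + 585×0.010 = 227.2 + 5.9 = 233.0. The counts are random, and the chance moves in a sawtooth with n: for the CT 90% bound at true 95% it is 50.8% at n=152, 64.3% at n=153, 63.5% at n=154 and 55.7% at n=165. There is about a 44% chance of 152 or fewer CT positives. The chance in step 3 was therefore averaged over the count, taken as the sum of two binomials at the planned prevalences.

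| Requirement (bound only) | Positives | True 95% | 96% | 97% | 98% |
|---|---|---|---|---|---|
| CT 510(k), ≥90% | 100 | 43.6 | 62.9 | 81.8 | 94.9 |
| CT 510(k), ≥90% | averaged | 58.1 | 79.3 | 93.7 | 99.2 |
| CT or TV CLIA, ≥89% | 120 | 60.6 | 79.4 | 93.0 | 98.9 |
| CT CLIA, ≥89% | averaged | 73.5 | 89.5 | 97.6 | 99.8 |
| TV CLIA, ≥89% | averaged | 90.9 | 98.3 | 99.9 | 100 |
| TV 510(k), ≥85% | 100 | 93.7 | 98.1 | 99.7 | 100 |
| TV 510(k), ≥85% | averaged | about 100 | about 100 | about 100 | about 100 |

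**5. Counts the plan treats as passing.** At the 81 unlisted counts, the chance on the CT 90% bound at true 95% runs from 45.0% (n=119) to 74.5% (n=192).

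**6. If the estimate must also be at least 95%.** The wording in 7.2 can be read that way. CT at n=100 and CLIA at n=120 are unchanged. TV 510(k) at n=100 becomes 61.6/78.8/91.9/98.5%. The averaged figures for either bound become about 52.5/75.0/91.8/98.9% for CT and 52.1/78.9/95.4/99.7% for TV.

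**7. True sensitivity for an 80% chance on the CT 90% bound.** About 96.9% at n=100 and about 96.0% averaged over the count (about 96.2% with the estimate condition).

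**8. What holds.** For the TV 85% bound at true 95%, the chance is never below 90.8% over n=100-200. For specificity at true 95%, with 1750−154 = 1596 CT or 1750−233 = 1517 TV negatives, the chance of a bound of at least 90% is about 100%.

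**The case against.** The best defence is that this is precision-based sizing. Protocol 7.1 rules out formal testing, the grid is expressly over estimates, and the exceptions are cells of that grid. If the sentence means that the requirements are met when the observed estimate is at least 95%, the tables and lists support it. That stands as a defence of the tables. It does not rescue the sentence, whose condition concerns the device and follows a stated assumption about its performance; 7.2 also sets numerical criteria despite the absence of a test. Even on the observed-estimate reading, the condition is uncertain and the text does not say so: at true 95% the estimate falls below 95% with chance 38.4% at n=100 and 39.4% at n=120.

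Two further points stand. At n=100, an observed 95% is already a listed exception, so the 43.6% figure is partly foreshadowed; the averaged figures and the 81 unlisted counts are the fairer test. And the premise of at least 95% includes better devices: at true 97% the averaged CT chance is already 93.7%.

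A reader might infer that Table 3 is miscalculated, or that the trial is too small and must enrol more. The documents support neither. The table reproduces, and no target probability of success is stated against which the enrolment could be called inadequate. A reader might also quote the n=154 figure of 63.5% as the CT outlook; that count lies just past a jump in the sawtooth and flatters the design.

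**Conclusion.** The concern holds as an error of inference about a design property. There is no error of arithmetic. For a device at the assumed 95%, the chance of meeting the CT 510(k) bound is 43.6% at the goal count and 58.1% averaged over the expected count, and it stays below 75% at every count from 100 to 200. The CLIA bound at its goal of 120 has a 60.6% chance. The shortfall is concentrated near 95-96% true sensitivity, reaching just under 97% at the minimum CT count. It should not be extended to the TV 510(k) bound or to the specificity bounds, where the plan's confidence is justified.

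These figures assume independent specimens, the planned prevalences and site split, 1750 enrolled and every positive evaluable. They concern the bound alone except where the estimate condition is named. NG is outside this point, because the plan handles its sensitivity through staged reviews. No estimate, interval or decision rule is affected. The correction is worth making because this passage is the plan's justification for its CT and TV counts.

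**What to change.** In Protocol 7.2 and SAP 5:

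- State that the 95-99% in Protocol Table 3 and SAP Table 2 are observed estimates.
- Replace the concluding sentence, for CT and TV sensitivity only, with the chance of meeting each bound at true 95, 96, 97 and 98%, at each goal count (100 for 510(k), 120 for CLIA) and averaged over the expected random count, as tabulated above.
- Say whether the estimate itself must also be at least 95%, and give the lower figures if so.
- Add one line with the true sensitivity needed for an 80% chance on the CT 90% bound, and note that the chance moves in a sawtooth with the count.

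Keep both tables, the exception lists and the specificity statement. Enrolment, criteria and analysis stay as they are. The cost is one replaced sentence and one small table in each document; the only downside is a less favourable stated outlook for CT.
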